# Statistical Procedures:

The primary outcome for this study is the time to resolution of DKA. We will compare time to resolution of the DKA of patients who had glucose levels monitored via DEXCOM G6 CGM and treated in the stepdown unit (both those enrolled in the retrospective study and those who will be enrolled in the prospective study) to DKA patients who had glucose levels monitored hourly via fingerstick (and not CGM) and treated in the ICU setting.

We will perform a non-inferiority trial to study whether monitoring glucose levels via CGM in DKA patients treated in the stepdown unit is not inferior to DKA treated patients in the ICU setting with hourly fingerstick glucose monitoring.

For a noninferiority trial, based on what we have previously observed for the time to resolution of DKA, and a noninferiority margin of 1/2 the SD, we estimate that a sample size of 98 patients per group will have a 90% power to determine noninferiority at an alpha level of 0.05. Since we enrolled 48 patients in the retrospective part of the study, we will need additional 50 patients enrolled in the prospective part of the study to have 90% power and a noninferiority at an alpha level of 0.05. We plan a conservative approach where we will enroll additional 50 DKA patients who will have glucose levels monitored via CGM. We will compare with the historical control using 1:1 matching, thus will collect historical control data which include DKA patients treated for DKA in the ICU setting with hourly fingerstick glucose monitoring.

We will perform linear regression (for patients enrolled in both retrospective and prospective part of the study) to learn what clinical factors are associated with length of time to the DKA resolution. Then we will use propensity matching for historical control group (DKA patients treated in the ICU setting with glucose levels monitored via hourly fingerstick glucose levels).

To study the frequency of hypoglycemic episodes (<70 mg/dl) in patients from both prospective and retrospective study; we will use CGM glucose data stored manufacture's web based software : Clarity.

We will also evaluate frequency of hypoglycemic episodes (glucose level <70%) in historical control patients who were treated for DKA in the ICU and had hourly glucose level monitoring.

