In order to have glucose levels sent from the transmitter to the DEXCOM app, each patient needs to have a user name and a password. A user name and password for each patient is created by the research team. Patient's information is coded when transmitted to these phones, meaning that instead of referencing any PHI such as MRN to identify the patient, the patient is labeled via a unique study-specific identifier ("study participate 001"). If the phones were to get lost, there will be no concern for improper release of PHI. The "study smartphone for the patient " is placed on the IV pole next to insulin infusion bag.

2. A study coordinator will set app DEXCOM follow apps (which are necessary for glucose to be sent from the patient study phone) on the study smartphones given to the nurse and provider for remote glucose monitoring.

There is a 2 hour "warm up" period until glucose levels are transmitted the study patient smartphone and during that time glucose levels should be checked via hourly fingerstick as per the DKA protocol.

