- 3. Once glucose levels are transmitted to the study smartphone devices, glucose levels from the CGM to guide insulin adjustments. Check fingerstick glucose if CGM glucose levels are <100 mg/dl and >350 mg/dl to guide treatment decisions. Note that CGM device will have audible alerts if glucose level are < 100 mg/dl and >350 mg/dl. If there are NO glucose levels transmitted to the phone please check q 1 fingerstick glucose levels and contact [name] ([name]). If CGM glucose data cannot restored and patient needs g 1 hour fingerstick glucose testing, patient will be transferred to the ICU. If patient is moved to the ICU the CGM will be removed. Although CGM data will be transmitted to the study smartphone devices continuously, please monitor CGM glucose levels every 1 hour and make treatment decisions based on q 1-hour CGM readings or more frequently when glucose levels are <70 mg/dl (confirmed with a fingerstick glucose). If patient's glucose levels are <100 mg/dl on the CGM, fingerstick glucose testing will be performed to ensure that fingerstick glucose level is not in hypoglycemic range (<70 mg/dl). If patient's glucose levels are in hypoglycemic range (<70 mg/dl), fingerstick glucose levels testing will be performed as per hospital protocol until hypoglycemia resolves. Once hypoglycemia resolves, then glucose levels from the CGM can be used for further insulin adjustments. In the Emergency Department, document glucose levels q 2 hours as per the research protocol or more frequently as per provider request treating the patient. When patient is transferred to the stepdown unit, glucose levels should be recorded every 3 hours in hospital electronic medical record system.
- 4. If the patient condition worsens and patient requires the ICU care, patient will be transferred to the ICU. Also, if patient needs to get MRI or CT, sensor and transmitter will be removed prior to the imaging.
- 5. Smartphones which are receiving glucose data (study provider smart phone, study nurse smart phone and the study patient smart phone which receives glucose level from the sensor and is next to the IV insulin bag) should be transferred to the Stepdown Unit nurse when patient is arrives at the Stepdown Unit.

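### Hypoglycemia in CGM patients is to be counted from the Clarity sensor record alone, which has gaps (warm-up, ICU transfer, CT/MRI) that the control record does not have

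*Combined protocol and SAP*

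**What the plan says.** **Outcome source.** For the retrospective and prospective CGM patients, Statistical Procedures states: "we will use CGM glucose data stored manufacture's web based software" (the product named is Clarity). For controls, the same section looks at episodes "in historical control patients who were treated for DKA in the ICU and had hourly glucose level monitoring".

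**When the sensor is silent or off** (Study Procedures, Prospective Study):
- Item 2: a 2-hour warm-up, during which glucose is checked by hourly fingerstick.
- Item 3: when sensor data are lost for good and hourly fingersticks become necessary, care moves to the ICU, with this consequence for the device: "If patient is moved to the ICU the CGM will be removed".
- Item 4: clinical worsening is a second reason for moving a patient to the ICU. For imaging, the rule reads: "if patient needs to get MRI or CT, sensor and transmitter will be removed prior to the imaging". Re-insertion is not mentioned.

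**Chart review.** The retrospective procedures describe the EMR search as serving time to DKA resolution and matching, with a general line that relevant data come from chart review. The prospective procedures reuse that process. Neither assigns EMR glucose values to the hypoglycemia outcome.

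**Status.** Study Design lists hypoglycemia as a secondary outcome. The Study Purpose and Rationale nevertheless names its incidence, beside time to resolve DKA, as a measure of non-inferiority.

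**Not stated.** The plan gives no observation window or exposure denominator for hypoglycemia, and no rule for analysing prospective patients who are transferred to the ICU. Study Design leaves 2 CGM patients of the quality-improvement project out of the analysis because they were treated in the ICU.

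**The concern.** An outcome can be counted only where its source is recording. In the CGM group the source is a device that the protocol itself takes off at defined moments, while glucose testing goes on by other means. Item 3 shows this most clearly: the patient is transferred precisely because hourly fingersticks are still needed, so monitored treatment continues after the sensor record has ended.

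Two features make this more than a recording detail. First, the gap is one-sided, because controls have no sensor to lose. Second, part of it is informative. ICU transfer marks the point at which stepdown care with CGM has stopped working for that patient, either clinically or technically. The Potential Risks section names hypoglycemia from inaccurate readings or disabled alarms as a risk of the system, so a safety count should not stop when monitoring fails.

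At stake is the hypoglycemia comparison that would accompany any claim that stepdown care with CGM is no worse than ICU care.

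**Working it through.** The plan gives no expected rate, margin or test for hypoglycemia, so there is no figure to reproduce. The check has two parts.

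**1. Coverage under the stated rules**

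| Period | Clarity | Other glucose data in CGM patients | Matching gap in controls |
|---|---|---|---|
| 2-hour warm-up | none | hourly fingerstick | no |
| Signal loss to the phone | not stated | hourly fingerstick | no |
| After removal for CT/MRI | none; re-insertion not described | fingerstick or laboratory values in the EMR | no |
| After ICU transfer | none | ICU fingerstick or laboratory values in the EMR | no |

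Events before removal stay in Clarity; only later ones are lost. Unrecovered signal loss leads to ICU transfer, so those two rows largely overlap.

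**2. Possible size of the loss from early removal**

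From the documents: 48 retrospective + 50 prospective = 98 CGM patients, with removal rules documented for the 50 only.

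Assumed, because the documents give no figures:
- f = share of prospective patients with early removal, 5-20%
- r = their episode rate relative to other CGM patients, 1-3
- s = share of their episodes that fall after removal, 0.5 or 1
- the 48 retrospective patients have the same base rate and no loss

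Patients affected: 50 × 0.05 = 2.5 to 50 × 0.20 = 10.

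Share of episodes missed:
- among the 50 prospective patients: f·r·s / (f·r + 1 − f)
- in the pooled 98: 50·f·r·s / [50·(f·r + 1 − f) + 48]

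| f | r | s | Prospective 50 | Pooled 98 |
|---|---|---|---|---|
| 5% | 1 | 0.5 | 2.5% | 1.25/98 = 1.3% |
| 5% | 3 | 0.5 | 6.8% | 3.75/103 = 3.6% |
| 10% | 1 | 0.5 | 5.0% | 2.5/98 = 2.6% |
| 10% | 3 | 0.5 | 12.5% | 7.5/108 = 6.9% |
| 20% | 1 | 0.5 | 10.0% | 5/98 = 5.1% |
| 20% | 3 | 0.5 | 21.4% | 15/118 = 12.7% |
| 20% | 3 | 1 | 42.9% | 30/118 = 25.4% |

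For scale, suppose 10 of the 98 patients truly have one episode each (10/98 = 10.2%). The pooled loss is then 10 × 0.013 = 0.13 to 10 × 0.254 = 2.5 episodes, an understatement of 0.13/98 = 0.1 to 2.5/98 = 2.6 percentage points. Controls lose none by this route.

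Warm-up is outside this formula. It adds 2 uncounted hours per patient, but soon after presentation with glucose above 250 mg/dl, when a low is least likely.

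**The case against.** The strongest reply has four parts.

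- **Chart review may already cover it.** The general line on chart review leaves room for EMR glucose. That is fair, but the plan names Clarity for this outcome and describes the EMR search for other purposes. If both sources are intended, the analysis section should say so.
- **Few patients may be affected.** The removal rules are documented only for the prospective part, and the exclusion criteria already remove patients with another clinical reason for ICU admission. This stands: it limits the size but does not close the gap.
- **Hypoglycemia is secondary.** The margin and sample size concern time to resolution only. This also stands, and it limits the weight of the point. The rationale still uses hypoglycemia to judge non-inferiority.
- **Continuous sensing works the other way.** A sensor can record lows that hourly fingersticks miss, and it does so through most of the monitored time. This stands as well.

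A reader might infer that the rule tilts the comparison in favor of CGM. The documents do not support a net direction: two opposing mechanisms are present and neither can be sized. A reader might also infer that the lost events belong to the patients who fare worst. That fits transfers for clinical worsening; nothing shows that patients who lose the sensor to imaging or technical failure are sicker.

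**Conclusion.** The concern holds in a limited form. Followed as written, the plan misses CGM-group events that only fingerstick or laboratory glucose would show during warm-up, after removal for CT/MRI and after ICU transfer, and controls have no such gap. For failed transmission to the phone, what Clarity retains is not stated.

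The size cannot be derived from the documents. With removal confined to the 50 prospective patients and the assumed ranges above, roughly 1% to 25% of pooled CGM-group episodes would be missed. The top of that range needs 20% early removal, a threefold episode rate and every such episode falling after removal. A modest loss is more likely. A loss of 3 in 10 episodes lies outside the pooled range. How sensors were handled in the 48 retrospective patients is not described, so no loss is claimed there.

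This is worth correcting because it follows from a stated rule, touches a safety outcome used in the rationale, and is cheap to repair. It does not show that the hypoglycemia comparison is biased toward CGM overall, and it does not bear on the primary outcome.

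**What to change.** Amend the hypoglycemia paragraph of Statistical Procedures as follows:

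1. Count episodes <70 mg/dl over the same defined window in both groups, for example from insulin start to DKA resolution, using the resolution criterion of the primary outcome. The sensor may stay on after resolution (item 6), so an undefined window would itself differ between groups.
2. For CGM patients, use Clarity plus EMR fingerstick and laboratory glucose, including warm-up, signal loss, time after CT/MRI removal and time after ICU transfer. Count a low seen by two sources once.
3. Keep transferred patients and their later events in the CGM group.
4. Report the hours covered by each source, and the rate per hour observed.
5. Add a sensitivity analysis using hourly-equivalent readings in both groups, to separate the coverage gap from the effect of continuous sampling.

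No clinical procedure changes, including the rules for sensor removal. The cost is a short amendment and some extra abstraction of values already in the EMR. The downside is that the CGM group's recorded rate may be somewhat higher.

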# Study Procedures:

### Retrospective Quality Improvement Project

We will search electronic medical records (EMR) for laboratory data and clinical notes to estimate time to resolution of the DKA. Laboratory data and patient's characteristics which can contribute to time to resolution of DKA will be needed to match historical controls (DKA patients treated in the ICU setting with and glucose levels monitored via hourly fingerstick). All relevant data will be gathered from chart review and stored in Excel format on a secure Department of Surgery server. All statistical analysis will be conducted in cooperation with Center for Innovation and Outcomes Research of the Department of Surgery.

#### Prospective Study

Patients who have glucose levels monitored by the CGM will be treated in the Stepdown Unit instead of intensive care unit (ICU) setting. Glucose levels from the CGM will be transmitted to the smartphones devices which will be provided to the provider and nurse taking care of the patient by the study team.

We provided extensive training for the ED staff and Stepdown Unit staff regarding the use of CGM in patients with DKA. Additionally, we will provide information sheet describing provider and nurses' role when DKA patients are monitored via CGM.

Once provider and the nurse in the ED give verbal consent for the study, and patient gives a written consent, a research coordinator will attach CGM DEXCOM G6 device (which consists of sensor and transmitter) on patient's arm and set up smartphone devices (study patient smartphone, study provider smartphone and study nurse smartphone) to receive glucose levels from the CGM device.

Description of the remote glucose monitoring via CGM device and workflow:

1. A research coordinator will apply sensor (which senses glucose levels just below the skin from the interstitial fluid) and transmitter (which gets glucose information from the sensor and send glucose information to the DEXCOM G6 app via Bluetooth to the smart phone provided by the study team) on the patient. The Dexcom CGM will be attached to the upper arm or lower abdomen. The patient will be asked for their preference. The Dexcom CGM should not be placed where the patient is lying down or sleeps. CGM will not be placed on scars, hair, tattoos, irritated areas, areas where the sensor can be rubbed (waist band, seat belt), and insulin injection sites. The patient may already be wearing their own personal CGM, which should not be removed. If the patient's personal CGM is on the arm, the study Dexcom CGM will be attached to the lower abdomen. If the patient's upper arm. The study patient smartphone receiving glucose level data needs to be placed on the patient's IV pole next to the insulin bag.

In order to have glucose levels sent from the transmitter to the DEXCOM app, each patient needs to have a user name and a password. A user name and password for each patient is created by the research team. Patient's information is coded when transmitted to these phones, meaning that instead of referencing any PHI such as MRN to identify the patient, the patient is labeled via a unique study-specific identifier ("study participate 001"). If the phones were to get lost, there will be no concern for improper release of PHI. The "study smartphone for the patient " is placed on the IV pole next to insulin infusion bag.

2. A study coordinator will set app DEXCOM follow apps (which are necessary for glucose to be sent from the patient study phone) on the study smartphones given to the nurse and provider for remote glucose monitoring.

There is a 2 hour "warm up" period until glucose levels are transmitted the study patient smartphone and during that time glucose levels should be checked via hourly fingerstick as per the DKA protocol.

- 3. Once glucose levels are transmitted to the study smartphone devices, glucose levels from the CGM to guide insulin adjustments. Check fingerstick glucose if CGM glucose levels are <100 mg/dl and >350 mg/dl to guide treatment decisions. Note that CGM device will have audible alerts if glucose level are < 100 mg/dl and >350 mg/dl. If there are NO glucose levels transmitted to the phone please check q 1 fingerstick glucose levels and contact [name] ([name]). If CGM glucose data cannot restored and patient needs g 1 hour fingerstick glucose testing, patient will be transferred to the ICU. If patient is moved to the ICU the CGM will be removed. Although CGM data will be transmitted to the study smartphone devices continuously, please monitor CGM glucose levels every 1 hour and make treatment decisions based on q 1-hour CGM readings or more frequently when glucose levels are <70 mg/dl (confirmed with a fingerstick glucose). If patient's glucose levels are <100 mg/dl on the CGM, fingerstick glucose testing will be performed to ensure that fingerstick glucose level is not in hypoglycemic range (<70 mg/dl). If patient's glucose levels are in hypoglycemic range (<70 mg/dl), fingerstick glucose levels testing will be performed as per hospital protocol until hypoglycemia resolves. Once hypoglycemia resolves, then glucose levels from the CGM can be used for further insulin adjustments. In the Emergency Department, document glucose levels q 2 hours as per the research protocol or more frequently as per provider request treating the patient. When patient is transferred to the stepdown unit, glucose levels should be recorded every 3 hours in hospital electronic medical record system.
- 4. If the patient condition worsens and patient requires the ICU care, patient will be transferred to the ICU. Also, if patient needs to get MRI or CT, sensor and transmitter will be removed prior to the imaging.
- 5. Smartphones which are receiving glucose data (study provider smart phone, study nurse smart phone and the study patient smart phone which receives glucose level from the sensor and is next to the IV insulin bag) should be transferred to the Stepdown Unit nurse when patient is arrives at the Stepdown Unit.
- 6. Sensors and transmitters are removed on the day of transfer to the hospital ward from the stepdown unit or 10 days from insertion (whichever comes first). The reason the sensors are not be removed at the resolution of DKA is that in case anion gap (AG) reopens (which indicates that patient is in DKA) then we can continue to monitor glucose levels using the sensor in place. Both sensors and transmitters will be removed by the primary nurse. The study smart phones are be returned to the research team (research coordinator) once DKA resolves.

The same process of abstracting data and demographic information described for the retrospective study from the patient's medical records for analysis will be used.

Provider Survey

We will identify nurses via EMR who took care of DKA patients who had glucose levels monitored via DEXCOM G6 CGM. We will then send them e-mail asking to voluntarily participate in the survey. The link to the anonymous QUALITRIC survey will be included in the e-mail.

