Continuous glucose monitoring (CGM) is widely used in the outpatient setting but its use is still investigational in the inpatient setting. Several studies showed improvement in detection of hyperglycemic and hypoglycemic episodes with the use of CGM when compared to fingerstick point of care (POC) glucose testing in both the ICU and non-ICU setting (5-8). The FDA has allowed use of DEXCOM G6 CGM in hospitalized patients during the COVID-19 pandemic (9). In a recent pilot study performed during the COVID-19 pandemic done in hospitalized patients in the perioperative period, DEXCOM G6 CGM showed a mean absolute relative difference (MARD) of 9.4% compared to point of care (POC) glucose measurements (10). Use of continuous glucose monitoring has not been reported in hospitalized patients with DKA. The DEXCOM G6 CGM (https://www.DEXCOM G6.com/) provides glucose levels in real time, as well as glucose trends, and alarms if glucose levels are in hypoglycemic or hyperglycemic range. These safety features can decrease the risk of hypoglycemia when patients with DKA are being treated with insulin infusion. Furthermore, the DEXCOM G6 CGM is labeled as an "integrated continuous glucose monitoring system" which can reliably and securely transmit glucose data to digital devices allowing remote monitoring of glucose levels by multiple care team members without entering patient's room and thus reducing the number of healthcare contact and use of personal protective equipment (PPE). If CGM is shown to be non-inferior to fingerstick glucose monitoring (measured by time to resolve DKA, incidence of hypoglycemia) in patients with DKA, then hemodynamically stable non-intubated DKA patients would not have to be transferred to the ICU for frequent fingerstick glucose testing as is now being done. Instead, these patients could be treated and monitored with CGM on the stepdown unit. This would help reallocate critical care unit beds, save time and effort for the nurses and help conserve PPE.

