## Potential Risks:

The potential risks of this prospective study include a breach in confidentiality given information will be shared across technology platforms. This breach of confidentiality is highly unlikely as all PHI will be stored in encrypted devices and on encrypted endpoints to which only the study investigators and those directly involved in patient care will have access

Risks associated with use of the system may include hypoglycemia (low blood sugar) or hyperglycemia (high blood sugar) in cases where information provided by the device is inaccurate and used to make treatment decisions or where hardware or set-up issues disable alarms and alerts.

There may be slight pain or bruising in the insertion site of the sensor. There is also a small risk of infection at the insertion site. We will use only skilled individuals to insert the device.

Patients may also experience skin irritation or redness around the device's adhesive patch

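### No planned analysis tests CGM accuracy in DKA: the protocol schedules no independent glucose check while the sensor reads 100-350 mg/dl, and CGM-group hypoglycemia is counted from unconfirmed sensor data

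*Combined protocol and SAP*

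**What the plan says.** Study Procedures, Prospective Study, item 3, puts insulin adjustment on the sensor after warm-up: "Once glucose levels are transmitted to the study smartphone devices, glucose levels from the CGM to guide insulin adjustments". The same item sets the bedside check: "Check fingerstick glucose if CGM glucose levels are <100 mg/dl and >350 mg/dl to guide treatment decisions". The word joining the two limits can only mean 'or'. The alarms use the same device and the same cut-offs: "Note that CGM device will have audible alerts if glucose level are < 100 mg/dl and >350 mg/dl".

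Fingersticks are called for in three other situations:
- **Warm-up, 2 hours** (text after item 2): "during that time glucose levels should be checked via hourly fingerstick as per the DKA protocol".
- **Signal loss** (item 3): "If there are NO glucose levels transmitted to the phone please check q 1 fingerstick glucose levels".
- **Hypoglycemia** (item 3): fingersticks are repeated under the hospital protocol until it resolves, and bedside values below 70 are confirmed by fingerstick.

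Statistical Procedures takes the hypoglycemia count for CGM patients from the sensor's stored data: "we will use CGM glucose data stored manufacture's web based software : Clarity". It does not ask for fingerstick confirmation. The historical controls were monitored by hourly fingerstick.

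Potential Risks lists hypoglycemia or hyperglycemia "in cases where information provided by the device is inaccurate and used to make treatment decisions". Study Purpose and Rationale gives one accuracy figure, a MARD of 9.4% against point-of-care glucose in perioperative inpatients, and says of the population studied here: "Use of continuous glucose monitoring has not been reported in hospitalized patients with DKA". Data and Safety Monitoring deals only with the protection of stored health information.

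**The concern.** The sensor under evaluation largely decides when it is checked, and it also supplies the safety outcome. If true glucose is low while the display is in range, the protocol calls for no check and the Clarity count records no event. If the display is between 70 and 99, the bedside fingerstick may find the low, but the planned outcome still does not count it.

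This matters because Study Purpose and Rationale makes incidence of hypoglycemia one of the two measures of non-inferiority, and draws from it the conclusion that stable DKA patients need not go to the ICU. Accuracy in DKA is unreported by the plan's own account, and nothing in the plan would measure it. A finding of similar hypoglycemia in the two groups could therefore reflect sensor error, and a finding of excess could too.

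**Working it through.** **What each check can show**

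| Situation | Reference check in the protocol | Usable against a CGM value? |
|---|---|---|
| Warm-up | hourly fingerstick | No, nothing is transmitted yet |
| Signal loss | hourly fingerstick | No, no value is transmitted |
| CGM <100 or >350 | fingerstick | Yes, but selected by the CGM |
| During hypoglycemia | repeated fingersticks | Yes, but selected |
| CGM 100-350 | none scheduled | None by protocol |

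The plan makes no calculation on this point, so there is no planned figure to reproduce. Its sample size has no bearing here.

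**Inputs.** From the documents: MARD 9.4%, triggers at 100 and 350 mg/dl, hypoglycemia below 70 mg/dl. Assumed: relative error is normal; MARD of 15%, 20% and 25%; bias of 0 or +20%. The documents give no accuracy figure for DKA, so the assumed values only show a range.

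**Step 1, error SD.** For a normal error with mean zero, MARD = SD x sqrt(2/pi) = 0.798 x SD. So SD = 0.094/0.798 = 0.118. The other three values are 0.15/0.798 = 0.188, 0.20/0.798 = 0.251 and 0.25/0.798 = 0.313.

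**Step 2, a low missed by the trigger.** P(display >=100 | true g) = P(Z > (100/g - 1 - bias)/SD). For g = 69, 100/69 - 1 = 0.449.

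| MARD | True 69, no bias | True 69, bias +20% | True 60, no bias |
|---|---|---|---|
| 9.4% | 0.007% | 1.7% | about 0% |
| 15% | 0.8% | 9.2% | 0.02% |
| 20% | 3.7% | 16% | 0.4% |
| 25% | 7.6% | 21% | 1.7% |

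These are chances per reading, not per episode.

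**Step 3, the Clarity count near 70, at MARD 9.4% with no bias.**
- True 65 shown as >=70: (70/65 - 1)/0.118 = 0.65, so about 26% of readings. A true low is not counted.
- True 75 shown as <70: (70/75 - 1)/0.118 = -0.57, so about 29% of readings. A false low is counted.

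**Step 4, errors well inside the range.** At a true 200 with no bias, the error exceeds 20% in 9% of readings at MARD 9.4% and in 43% at MARD 20%. Most such readings stay within 100-350 and call for no check.

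**The case against.** The strongest reply is that the protocol is protective where it matters. Readings below 100 or above 350 go to fingerstick, and the lower trigger sits 100 - 70 = 30 mg/dl above the hypoglycemia definition. At the only MARD in the documents, a true 69 almost never escapes it. Item 3 also describes continuous transmission with alarms, so an episode offers repeated chances to trigger unless errors persist from one reading to the next. All of this stands. It depends, however, on the perioperative accuracy carrying over to DKA, which is the quantity left unmeasured.

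Three stronger readings are tempting, and the documents do not support them.
- A reader might infer that CGM error cannot be detected at all. Readings outside 100-350 are checked, so the gap is confined to readings inside that range.
- A reader might infer that a sensor reading persistently high would hide every low value. Even at an assumed +45%, a true 68 displays 68 x 1.45 = 98.6 and triggers a check; with the noise of MARD 9.4%, a true 69 escapes only about half the time.
- A reader might infer that the sensor count must understate hypoglycemia. Step 3 shows that unbiased noise also adds false events.

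It can also be said that hypoglycemia is a secondary outcome and that accuracy is a separate objective. That is fair as to rank, and it is why this is an improvement and not a fatal flaw. But the rationale relies on the hypoglycemia comparison, so its measurement needs support.

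Lastly, if laboratory glucose is drawn during treatment, clinicians have an independent value. The documents say that laboratory data will be abstracted, but they neither name glucose nor give a draw schedule, so this is open.

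**Conclusion.** The concern holds in a limited form. While the CGM transmits and reads 100-350 mg/dl, no independent check is scheduled; no comparison with a reference glucose is planned; and CGM-group hypoglycemia rests on unconfirmed Clarity data.

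The bedside exposure is negligible at the cited MARD (0.007% per reading for a true 69) and becomes material only at poorer accuracy (0.8% to 7.6% at an assumed MARD of 15% to 25%) or with bias. The effect on the outcome count is larger and does not need poorer accuracy: near 70, roughly a quarter or more of readings at a true 65 or 75 fall on the wrong side at MARD 9.4%. Its net direction cannot be predicted from the documents.

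The figures assume normal relative error and apply per reading. They illustrate the problem and do not estimate sensor performance in DKA. As planned, the hypoglycemia comparison cannot separate a true difference, or its absence, from sensor error.

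**What to change.** In Statistical Procedures, add two items.

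1. **A descriptive accuracy analysis.** Pair each fingerstick taken while the sensor is live with the nearest Clarity reading, within a stated maximum time gap. Do the same for each laboratory glucose where the chart has one; the sponsor should confirm that these exist. Cover the 50 prospective patients, and the 48 retrospective patients where times allow. Report MARD, bias, the number of pairs with reference <70 while the CGM reads >=100, and the number with reference >350 while the CGM reads <=350. Keep laboratory pairs separate from CGM-triggered fingersticks, which are a selected sample.

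2. **A reference-based hypoglycemia count.** Beside the Clarity count, report hypoglycemia from fingerstick or laboratory values <70, with one definition for CGM patients and historical controls. Show how many reference values each group contributed, because a shared definition does not equalize sampling. State in advance that the safety conclusion will be limited if the two counts disagree or reference values are few.

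The sponsor should also reconcile the risk stated in Potential Risks with Statistical Procedures, item 3 of the prospective workflow, and Data and Safety Monitoring. No bedside checking rule is proposed here.

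The cost is protocol wording and some extra abstraction from charts and Clarity files already in use, with no added blood draws. Some pairs will be noisy where draw times are imprecise, and there may be few pairs below 70.
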